5.0 Study Protocol

5.1 Study Materials

The SPRINTTM Peripheral Nerve Stimulator (PNS) System will be used by subjects in Group 1. Up to two SPRINT Systems (i.e. 1 lead per stimulator) will be used by each subject.

5.2 Concurrent Medications and Non-Drug Therapies

- Subjects in both groups will receive SMT, which may include medication and/or non-drug therapies.
- However, subjects in both groups should not perform any rehabilitation activities that may conflict with the
- device Instructions for Use (such as water therapy) during the study.

215 5.3 Patient Recruitment

211

226227

230

- Patients planned for nontraumatic TFA or TTA will be screened at the Vascular Clinic. A Waiver of
- 217 Informed Consent for Recruitment Purposes and a Waiver of Authorization for Recruitment Purposes will
- be submitted to the Institutional Review Board (IRB). Protected Health Information (PHI) will be used to
- 219 locate and review appropriate medical records (CPRS, and paper medical records) to determine study
- eligibility. If a patient appears to meet all eligibility criteria (see Eligibility, Section 5.4), then he/she will
- be contacted by study investigators and given information detailing study objectives, procedures, follow-
- 222 up encounters, assessments, and potential risks and benefits. If the patient agrees to participate, he/she will
- be asked to sign the Consent Form. Study staff will explain the process randomization, lead placement,
- data collection, and follow-up encounters. All baseline information and outcome measurements will be
- collected and recorded on the appropriate Case Report Forms.

5.4 Eligibility

5.4.1 Inclusion Criteria

Inclusion criteria are nontraumatic transfemoral or transtibial amputation (TFA or TTA, respectively) and age over 18..

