4.2.7 Patient Outcomes and Hospital Discharge Survey

Other secondary outcomes including time to prosthesis fitting, wound healing, incidence of neuromas, time to hospital discharge 30-day readmission rate, and hospital discharge survey will be documented from the electronic medical record and compared between groups.

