5.5.3 Visit 2B: Daily hospital evaluations until discharge

Subjects in both groups will be evaluated by study investigators daily until they are discharged. The length of stay is approximately 14 days for TFA per VASQIP 2016 quarter 4 data (Veterans Affairs Surgical Quality Improvement Program). Based on this data, subjects in Group 1 will likely be discharged 7 to 14 days after starting peripheral nerve stimulation. Group 1 subjects will be asked questions to re-assess the stimulation-evoked paresthesia coverage of the leg. Stimulator devices will be inspected to ensure appropriate function. Lead exit sites are inspected for skin irritation, infection, and inflammation. These risks will be minimized by using sterile leads and sterile technique. Maintenance, care of the leads and lead exit sites, and bandage changes will be performed as needed. Subjects in both groups will be evaluated for the presence of phantom sensations, as well as least, worst, and average PLP or RLP according to the Schedule of Study Procedures.

364 .

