- The duration of this investigation is expected to be 18-24 months. We anticipate enrolling 2-4 patients per 454
- month. Each patient's participation will last approximately 12 months. 455

Data Management 6.0

Sample Size

- The investigation seeks to broaden the knowledge of the effects of neuromodulation on acute post-operative 458
- pain in nontraumatic lower extremity amputation. The aim is to evaluate the feasibility of implementing 459
- PNS in TFA or TTA in the acute post-operative period. 16 subjects will be randomized into two groups 460
- 461 with 8 each. Sampling will not be restricted by race or gender. The sample size of 16 is expected to allow
- the investigators to conduct a cost-effective yet informative pilot study to assess the logistics of placing the 462
- 463 device as described in this protocol, evaluate safety, and report any clinically significant differences in
- primary and secondary outcomes between Treatment and Control Groups. The study outcomes will be 464
- 465 reported in nontraumatic TFA or TTA, many of which are secondary to dysvascular disease. Although this is a specific subset of all amputations that are performed, dysvascular disease accounts for a sizeable 466
- proportion of limb loss in the US with an estimated prevalence of 38-82% (24, 25). The results of this 467
- investigation will be used to refine the study design, recruitment, randomization, retention, and assessment 468
- 469
 - procedures, and ultimately develop a larger, multicenter, randomized controlled trial to further evaluate

470 treatment efficacy, adverse effects, and cost efficiency. To improve generalizability, subsequent

471 investigations will seek to include a wider subset of amputations which may be accomplished with the

472 addition of more study sites.

473

490

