6.2 Sampling and Randomization Procedures

Based upon historical data on amputations at the HHM-VAMC, there are estimated to be one to two 474 475 amputations per week that would qualify for enrollment in this study. Subjects will be screened for enrollment through the vascular surgery clinic. A considerable proportion of vascular clinic patients will 476

require lower extremity amputation and are usually scheduled for next day surgery due to the urgency of 477

presentation. Study investigators will conduct a chart review of potential subjects and complete Form 01-478

479 A (screening and demographic information). Based on the chart review, if a patient appears to meet all 480

eligibility criteria, then they will be contacted by study investigators for potential enrollment. If the patient

agrees to participate, they will be consented and randomized to Group 1 or Group 2. 481

482 Prior to the start of this study, a member of the study staff that is not involved with recruitment or data

483 evaluation will be responsible for generating a random string of group assignments long enough to fill all

anticipated spots in this study. The numbers will be placed in secure envelopes by blocks of two. A block 484

485 of two will contain one assignment to the Treatment Group and one assignment to the Control Group. As

486 subjects are consented and enrolled in the study, they will be assigned an envelope which randomizes them

487 to a group. Subjects are not blinded to their group assignments. Subjects in the Treatment Group will

receive the investigational treatment (30 to 60-days of peripheral nerve stimulation) in addition to SMT. 488

489 Subjects in the Control Group will be treated with the SMT alone.

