6.3 Data Analysis

A table of outcome measures recorded during the study can be found in Appendix. Scores rating daily 491 492 average, worst, and least pain will be compared between groups. Changes in pain will be evaluated for

individual subjects and compared between groups. For each subject, mean pain scores over the first and 493

494 second months following TFA or TTA surgery will be calculated. An overall mean across all subjects will

be calculated. Additionally, sub-analyses will be performed to determine if there is a difference in these 495

outcomes between groups over different post-operative phases (such as acute (e.g. days 1-30) or subacute 496

497 (e.g., 1-3 months), or chronic (e.g. >3 months)). Statistical analysis will be performed with two-sample t-

498 test, and p-values will be reported without adjustment, consistent with feasibility study design and the

499 number of subjects.

500 Pain medication usage will be recorded in subject diaries and obtained during follow up encounters. Opioid

medication use will be analyzed by averaging 24-hour morphine equivalent dosing (MED) over each 501

502 follow-up interval and comparing groups. Changes in opioid medication use will be reported for individual

503 subjects by calculating morphine equivalent dosing (MED). Average MED will be calculated and compared between groups. The time to cessation of opioid use will be reported. Side effects associated 504

with opioid use will be assessed at each visit and the number of side effects occurring over various intervals 505

506 will be recorded. Analgesic-related outcomes will be compared between the Groups.

507 Patient Global Impression of Change (PGIC), Pain Catastrophizing Scale (PCS), and Pain Disability Index

508 (PDI) scores will be averaged for each group and compared. Data regarding functional outcomes

509 (Functional Independence Measure [FIM] score), time to wound healing, incidence of neuromas, prosthesis

fitting, time to hospital discharge, 30-day readmission rate, and hospital discharge survey will be compared 510

between groups. 511

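### Transfemoral and transtibial amputees are pooled with neither stratification nor a level term, so at 8 per arm one imbalanced trial could be misread on level-dependent outcomes, and some precision may be lost.

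*Combined protocol and SAP*

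**What the plan says.** - **Eligibility (5.4.1).** Both levels enter one trial: "Inclusion criteria are nontraumatic transfemoral or transtibial amputation (TFA or TTA, respectively". No quota or expected mix is given.
- **Size (Sample Size, under 6.0).** "16 subjects will be randomized into two groups" of 8. The same section intends to report clinically significant differences between the arms as well as feasibility.
- **Randomisation (6.2).** "The numbers will be placed in secure envelopes by blocks of two", and each block "of two will contain one assignment to the Treatment Group and one assignment to the Control Group". This balances the number per arm. No stratification factor is named.
- **Analysis (6.3).** "Statistical analysis will be performed with two-sample t"-test, with no covariate. The only sub-analyses are by post-operative phase. Nothing is tabulated or analysed by level.
- **Outcomes compared between arms.** Section 4.2.7 lists "Other secondary outcomes including time to prosthesis fitting, wound healing, incidence of neuromas" and time to discharge, among others. Section 4.2.6 compares improvement in FIM from a mobility baseline. Section 6.3 compares pain scores and within-subject changes in pain.
- **The one level-specific figure (5.5.3).** "The length of stay is approximately 14 days for TFA per VASQIP 2016 quarter 4 data". No TTA figure is given.

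**The concern.** Amputation level is a baseline factor known for every subject, and the plan uses it neither in the allocation nor in the analysis. Blocks of two fix the arm sizes at 8 and 8 but leave the split of TFA and TTA within each arm to chance. If an outcome differs by level, an uneven split puts part of that difference into the arm comparison. Even an even split leaves the variation due to level in the error term.

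The exposed outcomes are those where level plausibly matters and no baseline value can absorb it: time to prosthesis fitting and time to discharge. Mobility FIM is partly protected, because improvement from baseline removes a starting difference by level but not a different rate of recovery. At stake is a pilot difference that is attributed to PNS, and carried into the design of the larger trial, when part of it reflects which arm had more TFA subjects.

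**Working it through.** **Inputs from the documents:** 16 subjects, 8 per arm; one list of eight blocks of two; unadjusted two-sample t-test. No alpha, power, SD or effect size is stated, so there is no planned figure to reproduce beyond 8 + 8 = 16.

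**Assumptions, because the documents are silent:** TFA share p of 0.3 to 0.7; two-sided alpha 0.05; a TFA-TTA gap of L within-level SDs; or, equivalently, level explaining a share R² of outcome variance.

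**1. Chance imbalance.** With unstratified blocks of two, the TFA counts in the arms are independent Binomial(8, p). The exact distribution of their difference gives:

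| TFA share | 2 or more | 3 or more | 4 or more |
|---|---|---|---|
| 0.3 or 0.7 | 41% | 17% | 5.3% |
| 0.5 | 45% | 21% | 7.7% |

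**2. Shift in the arm difference.** An imbalance of k shifts it by (k/8) × L. For L = 1 this is 2/8 = 0.25 SD, 3/8 = 0.375 SD and 4/8 = 0.50 SD for k = 2, 3 and 4. The standard error in within-level SDs is √(1/8 + 1/8) = 0.50. So k = 3 moves the estimate by 0.375/0.50 = 0.75 of a standard error.

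**3. False-positive rate for a given split.** With no PNS effect (200,000 simulated t-tests per cell):

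| TFA split | L = 0.5 | L = 1 | L = 1.5 |
|---|---|---|---|
| 4 v 4 | 4.4% | 2.8% | 1.4% |
| 5 v 3 | 4.9% | 4.7% | 4.2% |
| 6 v 3 | 5.8% | 7.3% | 8.7% |
| 6 v 2 | 6.8% | 11.5% | 16.5% |
| 7 v 2 | 8.3% | 17.2% | 29.1% |

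Averaged over all randomisations at p = 0.5, the rate is 4.9% to 5.1%. Balanced splits run below 5% and imbalanced splits above it.

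**4. What a level term does to the 95% CI.** If level is balanced across arms, the width ratio (adjusted to unadjusted) is (t on 13 df / t on 14 df) × √(1 - R²), where 2.160/2.145 = 1.007. Without stratification, the level term also pays for its correlation with arm, so the ratio has to be simulated (60,000 trials per setting).

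| R² | Level balanced | No stratification (mean width) |
|---|---|---|
| 0 | 1.007 | about 1.045 |
| 0.1 | 0.956 | about 0.99 |
| 0.2 | 0.901 | about 0.93 |
| 0.3 | 0.843 | about 0.87 |

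**5. Stratifying as well (p = 0.5, 6,000 trials per setting).** The largest TFA difference between arms fell to 1, against 6 to 8 in the unstratified runs. Power for a 1 SD effect was:

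| Level gap | No stratification, no level term | Level term only | Both |
|---|---|---|---|
| L = 0 | 46% | 44% | 44% |
| L = 1 | 40% | 43% | 46% |
| L = 1.5 | 32% | 42% | 46% |

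**The case against.** **Randomisation already protects the comparison.** A reader might infer from the pooling that the planned t-test is invalid or biased toward PNS. It is not: the error rate over all randomisations stays at 5%, and the arms differ by at most one TFA subject in 55% to 59% of trials. What remains is narrower. Only one trial will be run, and the plan does not provide for showing whether it is one of the imbalanced ones.

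**The documents show no level effect.** This stands. The 14-day stay is quoted for TFA alone, so it shows no difference from TTA. The popliteal approach is offered for safety and patient response and is not tied to level. That fitting, discharge and mobility depend on level is plausible but assumed. The imbalance probabilities do not depend on it; the consequences do.

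**Pain is the primary outcome.** A reader might extend the point to pain. The documents give no reason for pain to depend on level, and 6.3 also examines within-subject change, which removes a baseline difference. The main point therefore does not rest on pain.

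**A level term is not free.** This stands too. In an unstratified trial with an imbalance of 3, the adjusted interval is about 4% to 6% wider at R² = 0.1 and 9% to 11% wider at R² = 0. The larger gains need level to be balanced across arms.

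**It is a feasibility pilot, and level is one of several prognostic factors.** This limits the weight. But the Sample Size section intends to report group differences, and level is a defined entry category known for everyone, so showing and using it costs little.

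**Conclusion.** The point holds in a limited form. Both levels are pooled, the allocation is not stratified by level, and the comparison has no level term. Given a TFA share of 30% to 70% (assumed), about one trial in five or six has an imbalance of 3 or more, which moves 3/8 of any level gap into the arm difference. The concern is the reading of one imbalanced trial, plus lost precision. It is not a systematic bias or an inflated overall error rate.

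It matters most for time to prosthesis fitting and time to discharge, which have no baseline value, and for mobility FIM. How much it matters depends on a level effect that the documents do not give. At 0.5 SD the false-positive rate for the splits examined is at most 8.3%; at 1.5 SD and 7 v 2 it is 29%. The change is worth making, with moderate weight for a pilot.

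**What to change.** 1. **6.2, only if the envelopes are not yet made:** prepare one series for TFA and one for TTA, using the planned level when randomisation precedes surgery. Cost: a possible 9 v 7 final split if both strata have odd counts. Blocks of two also stay predictable in an open-label trial; varied block sizes or minimisation by level would reduce that.
2. **6.3, in every case:** tabulate arm by level. This costs nothing.
3. **6.3, FIM improvement and time to discharge:** estimate the arm difference, with its 95% CI, from a linear model with arm and level. This uses one of 14 degrees of freedom.
4. **6.3, time to prosthesis fitting:** use a time-to-event comparison stratified by level that censors subjects not fitted. A linear model cannot handle subjects who are never fitted during follow-up.
5. **Pain:** add a level term as a sensitivity analysis only.

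Expected change in mean CI width from a level term in a linear model, without stratification: about -1%, -7% and -13% if level explains 10%, 20% and 30% of variance, and +4.5% if it explains none. With level balanced across arms: about -4% to -16% over the same range, and +0.7% if it explains none.

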5.4.2 Exclusion Criteria

- 231 Exclusion criteria are systemic infection, immunosuppressive disorder, implanted electronic devices,
- pregnancy, previous allergy to skin contact materials and/or anesthetic agent altered mental status, inability
- 233 to provide consent, greater than 180 morphine equivalents (MED) per day.

234 5.5 Study Plan

- The study includes 13 Visits. Please refer to the Appendix for a schedule of study procedures for both
- 236 groups as well as outcomes measured at each visit.
- Patients planned for nontraumatic TFA or TTA will be screened by the study investigators who are working
- on the Acute Pain Service (APS). APS is usually consulted for all transferoral and transtibial amputations
- 239 to provide perioperative anesthesia, which typically includes placement of a peripheral nerve catheter for
- local anesthetic blockade. When a potential subject is identified, study investigators will begin a chart
- review for screening purposes. The investigators will review the medical record of potential subjects and
- complete Form 00 (Screening and Demographic Information). Chart review will include the collection of
- name, social security number and date of birth from CPRS, the ORC, and the Vascular Clinic. Protected
- Health Information (PHI) will be used to locate and review appropriate medical records (CPRS and paper
- medical records) to determine study eligibility. If a subject appears to meet all eligibility criteria (see
- 245 incident records) to determine study engionity. If a subject appears to ineet an engionity enterta (see
- Section 5.4. Eligibility), then he/she will be contacted by study investigators and given recruitment
- 247 materials detailing study objectives, randomization, procedures, follow-up encounters, assessments, and
- 248 potential risks and benefits. The subject will be provided with patient information pertaining to the
- 249 peripheral nerve stimulator system under investigation. If permitted by the subject, a sponsor representative
- or their designee may be present at any of the study visits to advise on material handling and answer
- questions as needed.

Patients who are interested in participation will be asked to complete a Beck Depression Inventory (see Form BDI) to be screened for depression (must score 20 or less) prior to enrollment. Veteran participants who are evaluated by study staff and suspected to be depressed will be further evaluated by a psychiatrist or psychologist utilizing the Mental Health Consultation and Liaison Service at McGuire VAMC. Research study staff will page the C&L service at [name] (Use [name] after 4pm and on weekends) and then walk the participant to the C&L provider to facilitate the evaluation on the day that the participant

presents as depressed. If non-veterans participants are enrolled, arrangements made for him/her to be evaluated at a non-VA facility.

[figure not shown]

Figure 1 Subject flowchart.

258

259

260261

Patients who agree to participate in the study will be asked to sign the Consent Form. Ideally, patients should provide informed consent and be enrolled in the study prior to surgery. Typically, the local anesthetic peripheral nerve block catheters (or single shock femoral or sciatic nerve blockade) are placed on the day prior to surgery or day of surgery. Subjects will be given the opportunity to enroll in the study when the catheter is placed, however, those who wish to decide on enrollment after their surgery may be enrolled up until the time in which their peripheral nerve block catheter is removed, which is usually by post-op day 5. Upon enrollment, subjects will be evaluated by APS daily.

The Consent Form will be scanned into the electronic medical record. Consent for photographic and video recordings will be requested. If collected, photographs and videos are intended for potential use in publications, future grant applications, and educational purposes. Subjects will receive a copy of their consent forms if requested. HIPPA Forms will be signed. The Schedule of Study Procedures outlines the baseline information and outcome measures recorded at each "Visit" on Case Report Forms (CRFs). All completed paper documents will be securely stored in a locked box placed in a fixed, locked file cabinet in the Interventional Pain Clinic on 2C. Only authorized study personnel will have the keys to access study materials containing protected patient information. A note may be documented in the patient's electronic medical record to indicate participation in the study. Subjects will be randomized to Group 1 ("Treatment Group") or Group 2 ("Control Group") (see Section 6.2. Sampling and Randomization Procedures).

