4.0 Study Outcomes and Exploratory Measures

4.1 Primary Outcomes

4.1.1 Effect of PNS on acute pain after lower extremity amputation

The Brief Pain Inventory Short Form (BPI) is a 9-item questionnaire used to evaluate the severity of a patient's pain and the impact of this pain on the patient's daily functioning. The patient is asked to rate their worst, least, average pain, and rate the degree that pain interferes with general activity, mood, walking ability, normal work, relations with other persons, sleep, and enjoyment of life on a 10-point scale. Levels of PLP and RLP are re-assessed at follow-up Visits according to the Schedule of Study Procedures. Questions used to assess pain or sensation are listed below. For BPI #3, #4, and #5, responses are recorded on an 11-point scale from "0" to "10" with "0" defined as "No Pain" and "10" defined as "Pain as Bad as You Can Imagine."

- Check yes or no if you experienced any (phantom limb or residual limb) sensation in the last 24 hours
- BPI #3: "Please rate your (phantom limb or residual limb) pain by marking the box beside the number that best describes your pain at its **worst** over the last 24 hours."
- BPI #4: "Please rate your (phantom limb or residual limb) pain by marking the box beside the number that best describes your pain at its **least** over the last 24 hours."
- BPI #5: "Please rate your (phantom limb or residual limb) pain by marking the box beside the number that best describes your pain on the **average** over the last week."

4.1.2 Effect of PNS on the incidence and severity of chronic pain after lower extremity amputation

Chronic pain (i.e. pain persisting for more than 2 to 3 months after TFA or TTA surgery will be evaluated using BPI questions #3, #4, and #5 as above at follow-up Visits according to the Schedule of Study Procedures. Data will be compared between groups to assess for differences in the incidence and severity of chronic pain.

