5.5.4 Visits 3, 4 and 5: Weekly telephone follow-up evaluations

Visits 3, 4 and 5 consist of weekly telephone evaluations at 1, 2 and 3 weeks after starting peripheral nerve stimulation (Group 1) or discontinuation of peripheral nerve block (Group 2). If issues related to the peripheral nerve stimulator device or leads occur and cannot be resolved by telephone, subjects may be evaluated in the Interventional Pain Clinic as needed.

Subjects are asked to rate their worst, least, and average PLP and RLP (BPI #3, #4, and #5). A medical reconciliation will be completed during each phone evaluation by asking the subject how many pills of narcotic pain medications they have left and querying the Virginia Prescription Monitoring Program Database.

5.5.5 Visit 6: First outpatient clinic evaluation / 30 days after start of PNS

All subjects are asked to return to the Interventional Pain Clinic at 4 weeks after the start of peripheral nerve stimulation. Stimulator devices (Group 1) will be inspected to ensure appropriate function. Lead exit sites are inspected for skin irritation, infection, and inflammation. Maintenance, care of the leads and lead exit sites, and bandage changes will be performed as needed.

All subjects are asked to rate their worst, least, and average PLP and RLP (BPI #3, #4, and #5). Subjects will rate the degree with which pain has interfered with general activity, mood, walking ability, sleep, and enjoyment of life (BPI #9). Pain Disability Index (PDI) and Patient Global Impression of Change (PGIC) will be assessed. A medical reconciliation will be completed during each phone evaluation by asking the subject how many pills of narcotic pain medications they have left and querying the Virginia Prescription Monitoring Program Database.

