5.5.6 Visit 7, 8, and 9: Weekly follow-up telephone evaluations

Visits 7, 8, and 9 consist of weekly telephone evaluations at 5, 6, 7 weeks after starting peripheral nerve stimulation (Group 1) or discontinuation of peripheral nerve block (Group 2). If issues related to the

peripheral nerve stimulator device or leads occur that cannot be resolved by telephone, subjects may be evaluated in the Interventional Pain Clinic if needed.

Subjects are asked to rate their worst, least, and average PLP and RLP (BPI #3, #4, and #5). A medical reconciliation will be completed during each phone evaluation by asking the subject how many pills of narcotic pain medications they have left and querying the Virginia Prescription Monitoring Program Database.

5.5.7 Visit 10: Second outpatient clinic evaluation / up to 60 days after start of PNS

All subjects are asked to return to the Interventional Pain Clinic at approximately 60 days after starting peripheral nerve stimulation (Group 1) or discontinuation of peripheral nerve block (Group 2). Stimulator leads will be removed by gentle traction. The lead will be visually inspected by study staff to evaluate for lead fracture. In the case of a retained lead fragment, study staff will determine the most appropriate medical plan to further evaluate and treat the subject. In most instances, retained lead fragments do not need to be removed and are rarely associated with further complications. Lead exit sites are inspected for skin irritation, infection, and inflammation. Both groups will continue to be treated with SMT as needed until the end of participation in the study. Subjects in Group 1 are encouraged to complete the entire 60-days of peripheral nerve stimulation, however are free to discontinue treatment at any time during the treatment phase.

5.5.8 Visits 11, 12, and 13: Phone evaluations at 3, 6, and 12 months after study enrollment

Telephone evaluations for both groups occur at approximately 3, 6, and 12 months after study enrollment. Outcome measures to be assessed are listed in the Schedule of Study Procedures.

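### Section 5.5 lets a sponsor representative attend any study visit with no safeguard during unblinded self-reported scoring: an avoidable risk of differential reporting, mainly for the in-person scores up to about 8 weeks

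*Combined protocol and SAP*

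**What the plan says.** The permission is in the recruitment and screening paragraph of Section 5.5 (Study Plan). It opens "If permitted by the subject, a sponsor representative" and continues "or their designee may be present at any of the study visits to advise on material handling and answer" questions as needed. So there is a consent condition and a stated role. There is no restriction by arm, by type of visit or to device procedures, and no statement about outcome collection.

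The other relevant provisions are these.

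- Section 6.2: "Subjects are not blinded to their group assignments". No blinded or independent outcome assessor is described.
- Section 4.1.1, on the instrument for the primary outcomes: "The patient is asked to rate their worst, least, average pain". BPI interference, PGIC, PDI and PCS (Sections 4.2.1 to 4.2.4) are self-reports too.
- Section 5.1: the stimulator is for Group 1 only.
- Section 5.5.3: "Subjects in both groups will be evaluated by study investigators daily until they are discharged". Device and lead-site checks in Group 1 belong to the same evaluations as the pain ratings.
- Sections 5.5.5 and 5.5.7 with the Schedule of Study Procedures: at the Visit 6 and Visit 10 clinic attendances, device inspection or lead removal falls in the same visit as the BPI, PGIC, PDI and PCS.
- Sections 5.5.4, 5.5.6 and 5.5.8: Visits 3 to 5, 7 to 9 and 11 to 13 are telephone contacts.

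**The concern.** The permission is wider than its stated purpose. Advice on handling materials is needed when a lead is placed, checked, replaced or removed. It is not needed while a subject chooses a number from 0 to 10 or rates global improvement. A subject who knows the allocation and has a representative of the sponsor at the bedside may rate more favourably than otherwise. If that happens more often in one arm, it enters the between-group difference and cannot be separated from a treatment effect afterwards, because no attendance record is required.

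Section 1.2 makes assessment procedures one of the things this pilot is meant to test, and Section 6.3 plans between-group t-tests on the pain scores. A removable weakness in how those scores are taken therefore bears on both purposes.

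**Working it through.** The plan gives no figure to reproduce: Section 6.1 states 16 subjects, 8 per arm, without a significance level, standard deviation or target difference. The check is of where the exposure lies, followed by a sensitivity calculation on stated assumptions.

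**1. Visits.** Telephone: 3 + 3 + 3 = 9 of 13. The other four are Visit 1 (baseline), Visit 2 (lead placement in Group 1, daily inpatient evaluations in both groups), Visit 6 and Visit 10. Among Visits 3 to 13, pain is scored at 11, of which 2 (Visits 6 and 10) are clinic visits. The daily inpatient scores are additional. Section 5.5.3 expects discharge 7 to 14 days after stimulation starts, so the 1- and 2-week telephone visits may in practice fall during the admission.

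**2. Arms.** The permission names no arm. A role of advising on materials has almost no object in Group 2, so concentration in Group 1 is a reasonable inference, but only an inference. Section 5.5.1 says Group 2 is followed by telephone after discharge, whereas Sections 5.5.5 and 5.5.7 ask all subjects to return to clinic. If the former were followed, the later in-person scores would exist in Group 1 only.

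**3. How much of a shift would reach a mean score.** Let δ be the shift in a rating when the representative is present, *p* the share of averaged scores taken in person, and *a* the share of those attended. With equal weights and unaffected telephone scores, the bias is

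B = δ × (p₁a₁ − p₂a₂).

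The whole of δ arrives only if every averaged Group 1 score is in person and attended and no Group 2 score is attended.

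- Second month after surgery (Section 6.3), taken as days 31 to 60, with PNS started on day 7: Visit 6 is on day 7 + 28 = 35, Visits 7 to 9 on days 42, 49 and 56, and Visit 10 on day 7 + 56 = 63. One of four scores is in person. Taking Visits 7 to 10 instead also gives one of four. With a₁ = 1 and a₂ = 0, B = δ/4, so an assumed δ of 0.5 to 1 point becomes 0.125 to 0.25.
- First month: the weight of the daily inpatient scores is not stated. If each counts once beside Visits 3 to 5, p is 7/(7 + 3) = 0.70 to 14/(14 + 3) = 0.82. If only the numbered telephone visits count, p = 0.

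**4. What a given B would do.** Assumptions, none from the documents: two-sided α of 0.05, SD of 2 to 3 points, no true effect. With 8 per arm, SE = SD × √(2/8), which is 1.0 to 1.5 points. The noncentrality is B/SE on 14 degrees of freedom. The chance of a nominally significant result in favour of PNS is:

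| B (points) | SD 2 | SD 3 |
|---|---|---|
| 0 | 2.5% | 2.5% |
| 0.25 | 4.2% | 3.6% |
| 0.5 | 6.8% | 5.0% |
| 1 | 15.2% | 9.0% |

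The half-width of the 95% confidence interval is 2.1 points (SD 2) to 3.2 points (SD 3), so any shift considered here is small beside the random error.

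**The case against.** The strongest case against has five parts.

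- *The wording is only permissive.* The subject must agree, the representative may attend, and the role is limited. Nothing says the representative will attend or be present during scoring. This stands: the text shows a risk and no more. Consent, however, protects privacy and does not alter how a subject answers in company.
- *No arm is specified.* The sentence follows the handing over of device information at screening, and answering questions could apply to either group. This also stands. A reader might infer that attendance would be confined to Group 1 and that any shift would pass in full into the group comparison. The documents do not say so, and step 3 of the working shows how much would have to hold.
- *Most visits are by telephone.* True, and there is little reason for someone advising on materials to join a call. The permission literally covers those visits, since the protocol numbers them as visits, but the 3-, 6- and 12-month pain assessments are largely outside the concern. It would be wrong to infer that the chronic-pain outcome is compromised to the same degree.
- *The trial is open label anyway.* Unblinded investigators already assess pain and inspect devices in the same encounters, and the change proposed here would not remove that. It is still no reason to leave a second, removable source in place.
- *It is a 16-subject pilot.* This lowers the consequence. It does not remove it, because pain comparisons with p-values are planned and Section 6.1 intends to report clinically significant differences.

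**Conclusion.** The point holds as a cheap improvement. Section 5.5 permits sponsor attendance at any visit, subject to the subject's agreement, with no safeguard while unblinded self-reports are taken. If attendance follows the device, the resulting risk of differential reporting would favour PNS. The exposed scores are chiefly the daily inpatient ratings and those at Visits 6 and 10.

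The size is unknown. A reader might be tempted to express it as a fraction of a worthwhile difference, but the documents give neither a shift nor a target difference, so such a fraction would be one assumption divided by another. The table above is a sensitivity calculation and not an estimate: under its assumptions, the second-month case (B up to 0.25) raises the chance of a false result in favour of PNS from 2.5% to at most 4.2%, and a full 1-point shift would raise it to between 9.0% and 15.2%. Nor do the documents support saying that results will be biased.

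**What to change.** Amend Section 5.5 in three respects.

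1. Limit attendance by a sponsor representative or designee to lead placement, device checks and device trouble-shooting, still with the subject's permission.
2. State that BPI, PGIC, PDI and PCS are completed before the representative enters, or with the representative out of the room and off the call.
3. Record attendance on the visit form, and report it by visit and arm with the results.

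While doing so, reconcile Section 5.5.1 with Sections 5.5.5 and 5.5.7 on whether Group 2 is scored in clinic or by telephone after discharge, since this determines whether the in-person scores are comparable between arms.

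The cost is a sentence or two in the protocol, a tick-box on the form, and minor sequencing of inpatient and clinic visits so that questionnaires come before device work. Device support is kept.
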